5.5 Supply and Dosing

Each bottle of study medication will contain 64 capsules, sufficient for 28 days plus a 4-day overage in the event that any capsules are lost, accidentally destroyed, or there is a delay in the completion of the scheduled clinic visit. Each treatment day should consist of two (2) doses of study medication, one (1) capsule per dose in the morning and in the evening. If a dose is missed, the subject should take the missing dose as soon as possible, but should not “double up” doses, i.e., take 2 doses at one meal.

The subject and his/her parent/legal guardian will be instructed to administer study medication with meals and at least 8 ounces (240 mL) of fluid. All doses should be taken at least 5 hours apart. The parent/legal guardian should record the actual time the dose was taken in the electronic diary. If the dose was missed entirely, the parent/legal guardian should indicate the omission in the electronic diary as instructed. The study medication will be handled by authorized personnel and dispensed under the supervision of the Investigator or designated site personnel.

Each subject will receive one 64-capsule bottle of study medication at the Enrolment Visit (Day 1), and three bottles each at Visits 10, 12, and 14. The first dose of study medication will be administered in the clinic at the Enrolment Visit and the Study Coordinator will record this first dose.

Subjects should return the used bottle of study medication at each clinic visit for collection by site for drug accountability. If the study medication is not returned, the bottle of all unused study medication should be returned to the site at the subsequent office visit. The subject will be instructed to take the study medication only from the newly dispensed bottle. The last dose of study medication in this study will be taken on the day of End of Treatment (Visit 16).

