6.1.3 Treatment Period

The treatment period will begin at the Enrolment Visit on the day the first dose of study medication is administered (Study Day 1) and will end upon administration of the last dose.

Note: If at any time during the study, the subject discontinues from the study, the subject should be withdrawn from the study and complete the final visit of the treatment period (Visit 16) and the Follow-up Visit (Visit 17). All subjects who withdraw from the study after Visit 12 (Month 3) should have a final DXA assessment performed. The DXA assessment will only be required for subjects that were originally part of the DXA subgroup.

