6.1.4 Follow-up Period

The follow-up period lasts for 4 weeks following the final dose of study medication. AEs should be followed to assess their status and resolution during this timeframe. Any new concomitant medications should also be recorded.

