6.1.4.1 Follow-up (Clinical Assessment) – Visit 17 (Week 40/Day 281 +3 days)

The follow-up visit is scheduled to assess all AEs since the end of treatment to determine if resolution has occurred or update the ongoing status of these events. Also, any new events should be recorded. A review of the subject's concomitant therapy should be made to determine if any changes have been made.

At this visit, the following procedures will be performed:

- Review and update concomitant therapy;
- Review and record any new AEs and follow-up on any ongoing AEs;
- Vital signs including height and weight;
- Abbreviated physical examination;
- Collect blood and urine samples for clinical laboratory analysis (including a urine pregnancy test if applicable). A total of about 5.5 mL of blood will be collected for clinical laboratory analysis; and
- Collect electronic diary.

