6.3 Safety Evaluations

The following safety evaluations will be performed during the study to measure the safety of the study medication:

Adverse Events: AEs will be reported by the subject from the time of informed consent through the end of the follow-up period. AEs will be followed by the Investigator as determined by Sponsor or designee. Further details on AE reporting are provided in [Section 7](#). Any study medication related AEs persisting at the end of the study will be followed until resolution, or until a clinically stable endpoint has been reached.

In this study, faecal impaction and bone fractures will be captured as AEs. The events of faecal impaction will be used for the analysis of the fecal impaction frequency during the study (see [Section 8.6.2.5](#)).

Clinical Laboratory Tests: The following laboratory tests will be conducted and the appropriate Investigator shall determine the clinical significance of any out-of-range values.

- **Hematology Panel:** Hemoglobin, hematocrit, MCV, MCH, MCHC, RBC, WBC, white blood cell with absolute counts and percent differentials (neutrophils, lymphocytes, monocytes, eosinophils, basophils), platelet count.
- **Chemistry Panel:** Total cholesterol, triglycerides, glucose, total protein, albumin, alkaline phosphatase, AST, ALT, GGT, iron, LDH, total bilirubin, direct bilirubin, BUN, uric acid, creatinine, sodium, potassium, chloride, bicarbonate, calcium, phosphorus, magnesium.
- **Urinalysis:** Protein, glucose, ketones, occult blood, pH, specific gravity, color, appearance, leukocyte esterase, nitrite, bilirubin, and macroscopic examination. Microscopic examination will be done if abnormalities are present. Urine samples will be collected, when possible.

Physical Examination: Physical examinations will be conducted at various timepoints during the study. Any new post treatment findings or changes, as noted by the Investigator, will be reported as an AE.

Vital Signs:

Vital signs (including height and weight at designated visits) will be recorded during the study. Any post treatment clinically significant changes in vital signs (including weight) shall be noted by the Investigator and reported as an AE. Additional guidance regarding assessment of changes in blood pressure and heart rate are provided below.

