8.5.2 Adverse Events

The original terms used in the eCRF by Investigators to identify AEs will be coded to MedDRA® system organ class and preferred terms. Adverse events will be summarized in terms of incidence per dose group and overall. The incidence of an AE is defined as the number of subjects who experienced at least one episode during the study. Adverse event incidence rates will be summarized by system organ class (SOC) and preferred term (as determined by the coding).

Whatever the level of classification, if a subject experiences multiple episodes of an event within the given time reference, then the event is only counted once. Further, for summaries by severity or causality, the most severe event is chosen for a subject if that subject experiences multiple episodes of the same event.

In this study, faecal impaction and bone fractures will be captured as AEs. The events of faecal impaction will be used for the analysis of the faecal impaction frequency during the study (see [Section 8.6.2.6](#)).

AEs with onset dates after administration of the first dose of study medication or prior to the last day of treatment + 7 days will be considered treatment-emergent. Events with completely or partially missing onset dates will be included in the tabulations, unless the available partial date information clearly indicates that the event happened outside of the treatment period.

P-values from Fisher's exact test or chi-square test will be presented in the AE summary tables. The test will be performed to compare incidence rates at the SOC and "At Least One Event" level between the two treatment groups.

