8.5.3 Clinical Laboratory Tests

For clinical laboratory data, mean changes from pre-treatment to post-treatment visits will be summarized using descriptive statistics. Cross-tabulations analysis will be performed for laboratory parameters with reference normal ranges. The laboratory data will be categorized as low, within, and above the reference normal ranges. The summary tables will tabulate the number and percentage of subjects with pre-treatment values below/within/above the normal reference range versus minimum/maximum/final post-treatment values below/within/above the normal reference range. Normal reference ranges will also be provided in the summary display. Laboratory parameters that are not specified in the protocol will not be included in the analysis, but they will be provided in the individual subject listings.

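### With no treatment window in the laboratory shift tables, the final value is an off-drug Week 40 sample for subjects seen at follow-up and an earlier on-drug value for the rest

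*Combined protocol and SAP*

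**What the plan says.** Section 8.5.3 plans two summaries of laboratory data. First, "mean changes from pre-treatment to post-treatment visits will be summarized using descriptive statistics". Second, shift tables set each pre-treatment category against "minimum/maximum/final post-treatment values below/within/above the normal reference range". Neither *final* nor *post-treatment* is defined, and no visit or day limit is given.

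The timing comes from other sections:

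- The last dose is taken on the day of Visit 16 (Section 5.5), and the treatment period "will end upon administration of the last dose" (Section 6.1.3).
- Section 6.1.4 states: "The follow-up period lasts for 4 weeks following the final dose of study medication".
- The Schedule of Evaluations and Section 6.1.4.1 both call for blood and urine laboratory samples at Visit 17. It is the last of the scheduled samples (Visits 10, 12, 14, 16 and 17).
- Subjects who withdraw early are also asked to attend Visits 16 and 17 (Sections 4.5 and 6.1.1).

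Neighbouring analyses do set a period. In Section 8.5.2, adverse events with onset "prior to the last day of treatment + 7 days will be considered treatment-emergent". The listing of physical-examination changes in Section 8.5.4 is confined to the treatment period.

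**The concern.** Safety is the primary objective (Section 2.1), and change in laboratory parameters is a listed safety endpoint (Section 2.2.1). In a 36-week exposure study, a reader will take a final-value shift table as status at the end of exposure. Without a window it is not that, and it can mislead in either direction:

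- A value out of range at Week 36 that recovers off drug is shown as within range in the final column.
- A value that leaves the range only after stopping enters the final column, and may enter the minimum or maximum column. Under Section 5.7.1 the excluded medications may resume one week after the End-of-Treatment Visit, so such a value may reflect another treatment.

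The laboratory tables and the adverse event tables would also cover different periods without saying so.

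**Working it through.** The plan gives no figure of its own to reproduce here. The check is day arithmetic on the visit schedule, followed by an illustration on assumed inputs.

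**1. Which sample is final.** There are two direct readings of *post-treatment*:

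- After treatment has started. Section 6.3 uses the phrase this way: "Any new post treatment findings or changes, as noted by the Investigator, will be reported as an AE".
- After treatment has ended.

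Under either reading the last scheduled laboratory value is Visit 17. A subject without a Visit 17 sample contributes the last earlier one.

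**2. Time off drug at Visit 17.** Visit 16 is Day 253 + 3 (Schedule of Evaluations and Section 6.1.3.4). Visit 17 is Day 281 + 3 (Section 6.1.4.1).

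- Nominal: 281 − 253 = 28 days.
- Shortest: 281 − 256 = 25 days.
- Longest: 284 − 253 = 31 days.

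Section 3.1 gives Visit 16 as ±3 days. With that window the longest gap is 284 − 250 = 34 days.

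**3. Distance from the adverse event window.** Subtracting 7 days, the Visit 17 sample falls 18 to 24 days after a last-dose + 7-day window closes (18 to 27 with ±3).

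**4. Overlap with excluded medication.** The restriction ends at about Day 253 + 7 = 260. That is 281 − 260 = 21 days before the nominal Visit 17 sample.

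**5. What the minimum and maximum tables do.** A value above range on treatment puts that subject's maximum above range, and a value below range puts the minimum below range. Adding Visit 17 cannot reverse either. It can only add subjects whose first out-of-range value is off drug.

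**6. Illustration for the final-value table only.** Let p be the share out of range at end of treatment, a the share with a Visit 17 sample, and r the share of abnormal values back in range by Visit 17. Ignoring new off-drug abnormalities, the rate shown is p × (1 − a × r). None of p, a or r is in the documents. I assume p = 5%, so that 415 × 0.05 ≈ 21 subjects.

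| a | r | Rate shown | Subjects of 415 |
|---|---|---|---|
| 0.70 | 0.25 | 0.05 × (1 − 0.175) = 4.1% | 17.1 |
| 0.70 | 0.50 | 0.05 × (1 − 0.350) = 3.3% | 13.5 |
| 0.95 | 0.50 | 0.05 × (1 − 0.475) = 2.6% | 10.9 |
| 0.95 | 0.90 | 0.05 × (1 − 0.855) = 0.7% | 3.0 |

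The spread, from 4.1% down to 0.7% for the same true 5%, shows that the table's content depends on quantities the plan does not fix.

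**The case against.** The strongest reply is that the same sentence provides the safeguard. Every on-treatment out-of-range value appears in the minimum or maximum table, whatever happens by Week 40. The by-visit mean changes can show Week 36 on its own. Clinically significant laboratory changes become adverse events (Section 7.2.4), and liver enzyme increases are reportable within 24 hours (Section 7.2.1). All of this stands. A reader might infer that the plan hides a large part of the on-drug abnormalities. The documents do not support that: the masking is confined to the final-value cross-tabulation.

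Second, *final* is undefined. Sections 4.5, 6.1.1 and 6.1.3 call Visit 16 the final visit of the treatment period, so an end-of-treatment reading is possible. Section 8 also leaves further detail to a SAP, and the combined document contains no SAP text on laboratory windows. This stands in part: Visit 17 as the final value follows from applying the text, and is not an explicit rule. But Section 8.5.3 refers to final post-treatment values, not to the final treatment visit, and unlike several neighbouring sections it does not itself point to the SAP.

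Third, a reader might infer that off-drug abnormalities would be attributed to lubiprostone. The tables are descriptive and assign no cause; relatedness is judged event by event under Section 7.1.4. The fault is one of period, not of causal attribution.

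Fourth, the adverse event window is itself loosely worded. The *or* in the Section 8.5.2 sentence, read literally, removes the upper limit, and Section 7 defines treatment-emergent events with none. This is correct, so the fix has to repair that sentence too. The stated rationale for the excluded-medication change in Amendment 3 supports 7 days as the intent.

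**Conclusion.** The point holds for the final-value shift table and, more weakly, for the minimum and maximum tables. As written, the final column combines samples taken 25 to 31 days off drug with earlier on-drug samples. No other planned laboratory table gives category status at the end of exposure. The minimum and maximum tables lose nothing from the treatment period but can gain off-drug abnormalities.

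The size of the effect cannot be derived from the documents, and the rates in the working are illustrations only. The conclusion rests on the protocol text; a SAP that set a laboratory window would resolve it. This is an inexpensive improvement to a table that serves the primary objective, not a threat to the study's safety conclusions as a whole.

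**What to change.** Before database lock:

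1. In Section 8.5.3 and the SAP, define minimum, maximum and final over samples taken after the first dose and up to the last dose + 7 days. For completers the final value is then Visit 16.
2. For early withdrawals, use the last sample in that window and flag any termination sample taken later. The flag matters because Sections 4.5 and 6.1.1 set no time limit for the termination visit, and after Week 1 the clinic samples are 77 to 84 days apart (85 − 8, 169 − 85, 253 − 169). Excluding a late sample can therefore leave a much older value as final, or none at all for a very early withdrawal.
3. Tabulate Visit 17 in a separate off-treatment follow-up column.
4. In Section 8.5.2, change *or* to *and* in the treatment-emergent sentence, and align Section 7 with it.
5. Reconcile the Visit 16 window, which is +3 days in the Schedule of Evaluations and Section 6.1.3.4 and ±3 days in Section 3.1.

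The cost is a few lines of wording and one extra table column, with no new data. The downside is that some late termination samples move to the follow-up column.

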8.5.4 Physical Examinations

Subjects with changes from normal at baseline to abnormal during the treatment period in any organ system will be identified and listed. Shift tables, which indicate incidence rates of changes from (normal, abnormal) at baseline to (normal, abnormal) values at each visit, will be presented.

8.5.5 Bone Growth Assessments

Bone growth will be assessed on the DXA subgroup population (i.e., those subjects who were aged 6 to 9 or 14 to 17 at the time of enrolment into the SAG/0211PFC-1131 study, and who were qualified to participate and enrolled in the DXA substudy). Bone-related DXA endpoints will include:

- Percent changes from baseline in BMD and BMC;
- Change from baseline in BMD Z-scores and in height-adjusted Z-scores;
- Changes from baseline in height and weight Z-scores.

Details on analyses by age, race, and gender subgroups are provided in the SAP.

8.5.6 Vital Signs

Descriptive statistics will be provided to evaluate the changes from baseline for any vital signs, including height and weight, measured during the study.

8.5.7 Pharmacokinetic Evaluations

A population pharmacokinetic analysis will be performed using the concentration-time data from the sparse PK samples in this study. The analysis may include data from other studies with lubiprostone in adults, paediatric subjects, or healthy volunteers. A separate analysis plan for the population pharmacokinetic analysis will be prepared prior to database lock.

8.5.8 Subgroup and Exploratory Analyses

Upon completion of pivotal phase 3 studies, analyses of any under-represented subgroups such as males and non-whites will be performed on the pooled data from the pivotal studies. Details pertaining to these analyses will be specified in the SAP.

8.6 Analysis of Efficacy

8.6.1 General Inferential Principles

The following principles apply for all inferential analyses of efficacy: All tests are two-tailed at a significance level of $\alpha = 0.05$.

8.6.1.1 Missing Data

Details on handling of missing data are described in the SAP.

8.6.1.2 Multiplicity

No interim analyses will be performed and therefore no multiplicity adjustments will need to be made to account for them.

8.6.1.3 Multicentre Studies

Region and/or centre effects will be explored as detailed in the SAP.

8.6.2 Efficacy Endpoints

8.6.2.1 Overall and Monthly Change from Baseline in BM and SBM Frequency

Changes from baseline in BM and SBM frequency will be analysed overall, and at each month from Months 1 through Month 9. A month is defined as a 4-week period; e.g., Month 1 is Weeks 1-4; Month 2 is Weeks 5-8; Month 3 is Weeks 9-12. The SBM frequency rate per week will be computed as specified in [Section 8.6.2.1](#). The analyses of the months will utilize the same methods as those used in the analysis of weeks.

8.6.2.2 Overall and Monthly Change from Baseline in Incontinence Frequency

This analysis will be performed for subjects who are fully toilet-trained and for the subset of subjects presenting with incontinence at baseline. Change from baseline in incontinence frequency will be analysed overall, and at each month during Months 1 through 9 as described in [Section 8.6.2.2](#).

8.6.2.3 Overall and Monthly Change from Baseline in Production of Large Diameter Stool Frequency

This analysis will be performed for subjects who are fully toilet-trained. Change from baseline in the production of large diameter stool frequency will be analysed overall, and at Months 1 through 9 as described in [Section 8.6.2.2](#).

8.6.2.4 Overall and Monthly Change from Baseline in Proportion of BMs and SBMs in Toilet

This analysis will be performed for subjects who are fully toilet-trained. Change from baseline in the proportion of BMs and SBMs in the toilet will be analysed overall, and at each month during Months 1 through 9 as described in [Section 8.6.2.2](#).

8.6.2.5 Overall and Monthly Change from Baseline in Frequency of Faecal Impaction

Change from baseline in faecal impaction frequency will be analysed overall, and at each month during Months 1 through 9 as described in [Section 8.6.2.2](#).

8.6.2.6 Overall and Monthly Change from Baseline in Frequency of Retentive Posturing or Excessive Volitional Stool Retention

Change from baseline in retentive posturing or excessive volitional stool retention frequency will be analysed overall, and at each treatment month during Months 1 through 9 as described in [Section 8.6.2.2](#).

8.6.2.7 Overall and Monthly Change from Baseline in Constipation Signs and Symptoms

Mean changes from baseline will be generated based on subject reported data as to the degree of:

- Straining associated with SBMs;
- Stool consistency of SBMs;
- Abdominal pain associated with SBMs; and
- Constipation severity.

The following rating scales will be used:

Stool consistency: Modified Bristol Stool Form Scale (5-point scale);

Bowel straining: 0=Not at all, 1=A little, 2=Some, 3=Quite a bit, 4=Extremely

Constipation severity and abdominal pain: 0=Absent, 1=Mild, 2=Moderate, 3=Severe, 4=Very severe.

The overall change from baseline will be calculated as the baseline value subtracted from the average of all diary ratings, where the baseline value will represent the average rating during the 2-week screening period of the previous study (SAG/0211PFC-1131). The change from baseline for a week (7-day period) or month (4-week period) will also be calculated as the baseline value subtracted from the average of all diary ratings during a week or month.

Stool Consistency

The analysis of stool consistency will focus on consistency assessments associated with SBMs. The average stool consistency rating will be calculated for each month (4-week period), excluding measurements recorded within 24 hours after rescue medication intake.

Analyses will be based on the change from baseline, where the baseline value will represent the average stool consistency rating from all SBMs during the 2-week screening period of the previous study (SAG/0211PFC-1131). The van Elteren test using the change from baseline stratified by pool centre and stratified by study for the pooled group will be used.

Straining

Bowel straining will be analysed in a method similar to stool consistency.

Constipation Severity

The changes from baseline in mean constipation severity ratings at each month during Months 1 through 9 will be analysed. The change from baseline will be calculated as the baseline value subtracted from the average of all diary ratings during the given month. For these daily diary assessments, each month will be defined by 4-week intervals beginning with the day of the first dose of study medication (Day 1). For example, Month 1 will start with the daily assessment on Day 1 and end with the daily assessment on Day 29 (Week 4), Month 2 will start with the daily assessment on Day 30 and end with the daily assessment on Day 57 (Week

8), and Month 3 will start with the daily assessment on Day 58 and end with the daily assessment on Day 85 (Week 12). Each week will be defined by 7-day intervals beginning with the day of the first dose of study medication (Day 1).

The van Elteren test using the change from baseline stratified by pooled centre for the individual studies and stratified by study for the pooled group will be used.

Abdominal Pain

Abdominal pain will be analysed similarly to constipation severity. Summary tables for the monthly change from baseline will also be presented.

